4.3 END OF STUDY DEFINITION

A subject is considered to have completed the study if she has completed all phases of the study including the last visit shown in the Schedule of Activities (SoA).

Alternatively, a subject may be lost to follow-up or subject to withdrawal or early termination as described in Section 7.

5 STUDY POPULATION

5.1 INCLUSION CRITERIA

To be eligible to participate in this study, an individual must meet all of the following criteria:

- 1. Provision of signed and dated Informed Consent Form
- 2. Stated willingness to comply with all study procedures, including participation in follow-up visits and telephonic follow-up
- 3. Female aged 18 years and older
- 4. Indicated for Laparoscopic Hysterectomy (may include TLH, LAVH, robotic assisted vaginal hysterectomy)

5.2 EXCLUSION CRITERIA

An individual who, as per chart review, meets any of the following criteria prior to the procedure will be excluded from participation in this trial:

- 1. History of HIV
- 2. History of Hepatitis C
- 3. History of diabetes, that in the opinion of the investigator may delay healing
- 4. Current use of systemic corticosteroids

- 5. Active infection of genitals, vagina, cervix, uterus or urinary tract
- 6. Active bacteremia, sepsis or other active systemic infection
- 7. Presence of Sextually Transmitted Infection (STI)
- 8. Evidence of pelvic inflammatory disease (PID)
- 9. Known clotting defects or bleeding disorders
- Hemoglobin < 8 g/dL
- 11. Metastatic disease
- 12. On anticoagulant therapy
- 13. Participation in another interventional trial
- 14. Pregnancy
- 15. Abnormal PAP results that have not been fully evaluated, or in the opinion of the investigator may indicate risk of abnormal vaginal cuff healing
- 16. Co-morbidities that in the opinion of the investigator may indicate risk of abnormal vaginal cuff healing.

Additionally, an individual who meets any of the following intraoperative criteria during hysterectomy will be excluded from participation in this trial:

- 17. Bowel injury during laparoscopic hysterectomy procedure prior to attempted cuff closure
- 18. Bladder injury during laparoscopic hysterectomy procedure prior to attempted cuff closure
- 19. Cases in which, before study randomization, surgeon cannot identify adequate tissue along the cuff to apply suture laparoscopically
- 20. Cases requiring conversion to laparotomy prior to study intervention

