- 8. Evidence of pelvic inflammatory disease (PID)
- 9. Known clotting defects or bleeding disorders
- 10. Hemoglobin < 8 g/dL
- 11. Metastatic disease
- 12. On anticoagulant therapy
- 13. Participation in another interventional trial
- 14. Pregnancy
- 15. Abnormal PAP results that have not been fully evaluated, or in the opinion of the investigator may indicate risk of abnormal vaginal cuff healing
- 16. Co-morbidities that, in the opinion of the investigator, may indicate risk of abnormal vaginal cuff healing

Intra-operative Exclusion Criteria

- 17. Bowel injury during laparoscopic hysterectomy procedure prior to attempted cuff closure
- 18. Bladder injury during laparoscopic hysterectomy procedure prior to attempted cuff closure
- 19. Cases in which surgeon cannot identify adequate tissue along the cuff to apply suture laparoscopically
- 20. Cases requiring conversion to laparotomy prior to study intervention

Description of Sites/Facilities Enrolling Participants:

The primary sites in this study will be:

Thomas Jefferson University Hospital with locations at [name] and [name]; and

Hershey Medical Center, Penn State College of Medicine at [name].

Enrollment may take place at any of these locations.

There may be additional sites within or outside the United States added (but not more than three total institutions), based upon enrollment.

Description of Study Intervention:

The Zip-stitch™ Vaginal Cuff Closure System is a surgical wound closure system consisting of a series of clips and a reusable, re-sterilizable clip applicator. The clips are made of the bio-absorbable polymer poly-p-dioxanone (PDO) and maintain closure of the vaginal cuff during the healing process, then are ultimately absorbed by the body five to eight months after application.

Protocol QD-PRO-045 Rev 005

Indication for Use:

The Zip-stitch™ System's indication for use is to close the vaginal cuff

following laparoscopic hysterectomy.

Study Duration: Enrollment is intended to occur over three to five months and follow-up is

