6.5.1 RESCUE TREATMENT

In the event that a subject is enrolled, and a random treatment is assigned, but the surgeon is unable to achieve cuff closure with the assigned cuff closure method, the surgeon may close the cuff using an alternate method. This event would be considered a protocol deviation and these subjects will be included in analysis of the primary efficacy outcome. These subjects will also be included in secondary endpoint ITT and safety populations, and subject safety data will be included in study analysis.

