7.2 PARTICIPANT DISCONTINUATION/WITHDRAWAL FROM THE STUDY

Participants are free to withdraw from participation in the study at any time upon request. An investigator may discontinue or withdraw a participant from the study for the following reasons:

- Reported sexual activity prior to six-week follow-up;
- If any clinical adverse event (AE), abnormality, or other medical condition or situation occurs such that continued participation in the study would not be in the best interest of the participant; or
- If the participant meets an exclusion criterion (either newly developed or not previously recognized) that precludes further study participation.

Follow-up will continue for any subjects who are withdrawn from the study by an investigator for any of the above reasons. These subjects will remain part of the ITT population for the evaluation of the primary endpoint and will be included in the study safety population.

The reason for participant discontinuation or withdrawal from the study will be recorded on the End of Study Case Report Form (CRF). Subjects who sign the informed consent form and are randomized but do not receive the study intervention may be replaced. Subjects who sign the informed consent form, and

Protocol QD-PRO-045 Rev 005

are randomized and receive the study intervention, and subsequently withdraw, or are withdrawn or discontinued from the study, will not be replaced.

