9.3 POPULATIONS FOR ANALYSES

Intent-to-treat population (ITT): This population will include all subjects enrolled and randomized to test or reference treatment. Subjects will be analyzed according to the treatment to which they were randomized, regardless of the treatment they actually received.

Safety Population: This population will include all subjects enrolled and randomized to test or reference treatment. Subjects will be analyzed according to the treatment that they received; patients randomized to the reference arm that receive Zip-stitch™ will be included in the Zip-stitch™ safety population. Similarly, patients randomized to the Zip-stitch™ arm that receive sutures will be included in the reference safety population.

Primary and secondary efficacy analyses will be performed on the ITT population. All safety analyses will be performed on the Safety population.

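### Exclusions 17, 18 and 20 (and 19 in the synopsis) are not cut off at randomisation; this conflicts with the stated sequence and, with the replacement rule in 7.2, leaves room for selection after allocation

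*Combined protocol and SAP*

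**What the plan says.** The order of events is stated consistently. Section 4.1, section 6.3, the Schedule of Activities footnote and the intra-operative screening steps in section 8.1 all have the intra-operative criteria cleared before the woman is enrolled and randomised. Closure starts after that. Sections 4.2 and 6.3 acknowledge that the operating surgeon cannot be blinded.

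The intra-operative exclusions have different end points:

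- 17 (synopsis and 5.2): "Bowel injury during laparoscopic hysterectomy procedure prior to attempted cuff closure".
- 18 (synopsis and 5.2): "Bladder injury during laparoscopic hysterectomy procedure prior to attempted cuff closure".
- 19 in section 5.2: "Cases in which, before study randomization, surgeon cannot identify adequate tissue along the cuff to apply suture laparoscopically". In the synopsis: "Cases in which surgeon cannot identify adequate tissue along the cuff to apply suture laparoscopically", with no time limit.
- 20 (synopsis and 5.2): "Cases requiring conversion to laparotomy prior to study intervention".

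Five other provisions bear on a woman who has been randomised but not treated:

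- Section 7.2, replacement: "Subjects who sign the informed consent form and are randomized but do not receive the study intervention may be replaced". No reason is required, and nothing is said about whether the replaced woman is followed or counted.
- Section 7.2, withdrawal: an investigator may withdraw a participant who is found to meet an exclusion criterion, new or previously missed. Women withdrawn this way are followed and stay in ITT for the primary endpoint.
- Section 7.1: a subject discontinued by an investigator for a reason other than dehiscence may be left out of the study analysis.
- Section 9.3, on ITT: "This population will include all subjects enrolled and randomized to test or reference treatment".
- Section 6.5.1 covers the case in which "the surgeon is unable to achieve cuff closure with the assigned cuff closure method, the surgeon may close the cuff using an alternate method". Such women stay in the primary analysis, but section 9.4.10 sets their primary value to missing and imputes it.

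**The concern.** An eligibility criterion should stop operating when the envelope is opened. Criteria 17, 18 and 20 are tied to a later moment, the start of closure, and 19 in the synopsis is tied to none. Read literally, they can still be invoked between the opening of the envelope and the first clip or stitch, by a surgeon who now knows the assignment. The replacement sentence in 7.2 applies only after allocation, so checking eligibility beforehand does not limit it.

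What is at stake is the protection that randomisation gives. If the decision to take a woman out can depend on her arm, the arms may no longer be comparable. That affects the dehiscence comparison in section 3.1 and the secondary comparisons. The composition of the test arm also feeds directly into the implant-passing rate that is set against 5%.

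**Working it through.** **1. The plan's own sample size.** Section 9.2 and the synopsis give 35 evaluable test women, 10% loss and 2:1 allocation. 35 / (1 − 0.10) = 38.9, rounded up to 39 test; 39 / 2 = 19.5, rounded up to 20 reference; total 59, as stated. For the maximum, 40 / 0.90 = 44.4; the plan uses 44, which is also 40 × 1.1. Then 44 / 2 = 22 and the total is 66. Nothing in this point changes these figures.

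**2. Sequence against cut-offs.** The sequence is: criteria cleared, enrolment, envelope opened, closure begun. Only criterion 19 in section 5.2 ends at the envelope. Criteria 17, 18 and 20 end one step later in both places, and 19 in the synopsis has no stated end. The gap is the interval between envelope and closure.

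**3. The status of one woman.** Suppose a randomised woman meets criterion 17, 18 or 20 within that interval.

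- Under the exclusion lists she is excluded from participation.
- Under the replacement sentence in 7.2 she may be replaced.
- Under 7.1 she may be left out of the analysis.
- Under the withdrawal paragraph of 7.2, and under 9.3, she stays in ITT in her assigned arm.
- Under 9.4.10, if her six-week data are missing, she is not counted in the main primary denominator.

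The documents do not say which of these governs.

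**4. Sensitivity of the primary rule.** Section 3.1 requires an observed rate below 5%, with no statistical test.

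- 35 evaluable: 1/35 = 2.9% meets it; 2/35 = 5.7% does not.
- 40 evaluable: 2/40 = 5.0%, which is not below 5%.
- 41 evaluable: 2/41 = 4.9% meets it.
- 44 evaluable: 2/44 = 4.5% meets it; 3/44 = 6.8% does not.

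So at most 1 failure meets the rule with 30 to 40 evaluable test women, and at most 2 with 41 to 44. At 35, the binomial chance of 0 or 1 failure is 0.845 if the true rate is 2%, 0.472 at 5% and 0.122 at 10%.

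**5. Illustration on assumed figures.** None of these inputs is in the documents. Let 3 of 35 test women have a raised passing risk of 20% or 40%, and the other 32 a risk of 3%. The chance of at most one failure is ∏(1 − pᵢ) × [1 + Σ pᵢ/(1 − pᵢ)]. At 20% this is 0.8³ × 0.97³² × [1 + 3(0.25) + 32(0.0309)] = 0.193 × 2.740 = 0.53.

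- None replaced: 0.53 (risk 20%) or 0.33 (risk 40%).
- One replaced by a woman at 3%: 0.59 or 0.44.
- All three replaced: 0.72 in both cases.

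If the reason for removal is unrelated to passing, so that everyone is at 3%, the figure is 0.72 with or without replacement and there is no effect.

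**The case against.** The strongest reply is that the sequence is stated several times and is unambiguous. Section 5.4 also defines screen failures as women who were not randomised or entered. A reader might infer that the protocol permits exclusion after the envelope is opened. It does not say so: that reading contradicts the stated procedure. This stands, and it makes the point a conflict to resolve rather than an instruction to object to. It does not dispose of the replacement sentence, which concerns only women already randomised.

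A reader might infer that a replaced woman leaves ITT. Section 9.3 and the withdrawal paragraph of 7.2 point the other way, and 9.4.10 adds sensitivity analyses with missing ITT outcomes set to success and to failure. That also stands. The exposure is to the main primary denominator, through 7.1 or missing six-week data, and to the silence on what follows replacement.

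A reader might say that allocation concealment is defeated. It is not: the sealed envelopes, stratified by site with variable blocks, are unaffected. The issue is selection after allocation.

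A reader might picture difficult cuffs being moved out of the test arm. Criteria 17, 18 and 20 are bowel injury, bladder injury and conversion, which are discrete events. They may simply mark the operative phase, since section 4.2 speaks of complications during anaesthesia or colpotomy. Only 19 concerns cuff tissue, and section 5.2 already limits it.

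Finally, a reader might treat removal of one woman as turning 2/35 into 1/35. A test-arm woman removed before the first clip has no clip to pass, so the second failure is hypothetical.

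**Conclusion.** The wording should be corrected. The end points of 17, 18 and 20, and the missing one for 19 in the synopsis, conflict with the stated sequence. With the open replacement rule in 7.2 and the wording of 7.1, they leave a short interval in which an unblinded surgeon could exclude and replace a randomised woman, contrary to 9.3.

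The size of any bias cannot be estimated, because the documents do not say how often this would occur or whether these events relate to passing. On the assumed figures above, the effect on the chance of meeting the target ranges from nil to substantial. Sensitivity is high only because the primary rule turns on a single count: one permitted failure at 30 to 40 evaluable test women, two at 41 to 44. The documents support no claim that the sponsor intends such removals or that they would favour one arm.

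**What to change.** - In both the synopsis and section 5.2, end criteria 17 to 20 at randomisation, before the envelope is opened.
- State that every randomised woman stays in the ITT population in her assigned arm, is followed and is reported, whether or not she received the assigned device.
- In section 7.2, delete the permission to replace, or allow further enrolment only as additional subjects and never as substitutes.
- Reconcile section 7.1 with 7.2 and 9.3, so that one rule governs women discontinued by an investigator.

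These changes concern eligibility timing and analysis status only. Operative management after an injury or conversion, and the scope of section 6.5.1, are for the sponsor. That section covers only failed closure with the assigned method, so it should not be assumed to apply to these women.

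The cost is a few sentences, and the target of 59 stands. The small downside is that an occasional woman without the assigned device stays in that arm's ITT denominator, as 9.3 already requires. Because such a woman in the test arm has no clip to pass, she should be identified in the report: at the boundary, one extra woman in the denominator moves 2/40 = 5.0% to 2/41 = 4.9%.

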5.3 LIFESTYLE CONSIDERATIONS

Participation in study may require more hospital/doctor visits than would otherwise be necessary due to trial follow-up schedule, including one week, six weeks, and six months post-operative visits and a 12-month follow-up phone call. It is not expected that this will present an increased financial burden, but subjects will receive nominal renumeration for their time and travel.

As is required with all laparoscopic hysterectomy procedures, participating subjects will be required to abstain from sexual intercourse for a minimum of six weeks after their procedure.

5.4 SCREEN FAILURES

Screen failures are defined as participants who consent to participate in the clinical trial but are not subsequently randomly assigned to the study intervention or entered in the study. A minimal set of screen failure information is required to ensure transparent reporting of screen failure participants, to meet the Consolidated Standards of Reporting Trials (CONSORT) publishing requirements and to respond to queries from regulatory authorities. Minimal information includes demography, screen failure details, eligibility criteria, and any serious adverse event (SAE).

Individuals who do not meet the criteria for participation in this trial (screen failures) will not be rescreened.

5.5 STRATEGIES FOR RECRUITMENT AND RETENTION

This clinical trial will involve one test treatment (and a separate comparative reference treatment) administered at one or more investigative locations. As the treatment is part of laparoscopic hysterectomy procedures, recruitment and retention strategy will concern women above the age of 18 of all races and ethnicities who are intending to undergo laparoscopic hysterectomy. Subject

Protocol QD-PRO-045 Rev 005

recruitment will take place in the weeks to months prior to a procedure from the regular patient pool of each investigator. Patients intending to undergo laparoscopic hysterectomy around the time of the study, who are identified as meeting all pre-operative inclusion/exclusion criteria will be approached for participation by the responsible principal investigator. One out of four potential candidates are expected to enroll in this study.

Subjects will be approached for potential participation during a doctor visit as part of their normal medical care. It is not expected that this will present an increased financial burden, but subjects may be nominally remunerated for travel and inconvenience due to participation in this study. All subjects approached but not enrolled will be documented in the study's screening log.

6 STUDY INTERVENTION

6.1 STUDY INTERVENTION(S) ADMINISTRATION

6.1.1 STUDY INTERVENTION DESCRIPTION

The test device being evaluated in this study is the Zip-stitch[™] Vaginal Cuff Closure System, as described below.

6.1.2 STUDY AGENT DESCRIPTION

The Zip-stitch™ Vaginal Cuff Closure System is a system for closing the vaginal cuff following hysterectomy. The system includes a series of bioabsorbable clips, a reusable clip applicator, and a reusable clip loading tool. The clips are injection molded from polydioxanone (PDO) and sterilized with ethylene oxide. The applicator and loading tool are reusable surgical instruments made of stainless steel that facilitate delivery of clips to the treatment site.

The clips are inserted into the applicator outside the body using the loading tool, and the system enters the body cavity through a surgical trocar. Through use of the applicator handle, opening lever, and trigger, a clip is applied to interposed leaves of the vaginal cuff. Subsequent clips are applied to the surgical wound until the whole span of the wound has been closed. The clips provide mechanical support to the tissue during the healing process, and clips maintain soft tissue approximation for the critical wound healing period (14 days) while resisting postoperative forces. After this holding period, the clips degrade by hydrolysis and are absorbed by the body after approximately eight months.

All Zip-stitch™ system components will be provided by the study sponsor, ZSX Medical LLC, including Zip-stitch™ system training and methodology. Physical products will be shipped prior to study commencement. The surgical methodology developed for Zip-stitch™ closure of the vaginal cuff during laparoscopic hysterectomy will be provided with this clinical protocol as the device Instructions For Use. Zip-stitch™ system training will be provided by the sponsor ZSX Medical and will take place no longer than two weeks prior to the first procedure performed by each surgeon. Zip-stitch™ System training will involve review of the device Instructions for Use, recommended clinical technique, and an illustrative cuff closure video. Study training will also include discussion of expected technical challenges, such as proper technique for removal and replacement of Zip-stitch™ clips. After training is completed, sponsor representative and recipients of training will sign the training form.

All Zip-stitch[™] clips will be provided sterile and will be packaged and labeled appropriately for human use. Each clip will be packaged and labeled individually. Zip-stitch[™] clip application systems, including the Zip-stitch[™] reusable clip applicator and the Zip-stitch[™] reusable clip loading tool, will be provided

Protocol QD-PRO-045 Rev 005

packaged and unsterile, with instructions for sterilization prior to use included in the device Instructions for Use contained in packaging.

These Zip-stitch[™] products are not available anywhere except through the sponsor, ZSX Medical LLC, but are solely intended for human use as applied in this trial. The Zip-stitch[™] system has not yet been cleared by FDA. This study is being conducted under an Investigational Device Exemption. All devices will be labeled, "CAUTION: Investigational Device. Limited by Federal (or United States) law to investigational use."

The study reference device is VICRYL[™] suture in a running fashion, used according to product labeling. Reference device(s) should be used and stored according to their product labeling.

6.2 PREPARATION/HANDLING/STORAGE/ACCOUNTABILITY

6.2.1 ACQUISITION AND ACCOUNTABILITY

Test and reference device materials will be delivered to investigational site by the sponsor. Devices are to be handled and stored according to product labeling.

6.2.2 FORMULATION, APPEARANCE, PACKAGING, AND LABELING

Each Zip-stitch[™] Vaginal Cuff Closure System includes one stainless-steel reusable handheld laparoscopic clip applier and stainless-steel clip loading tool (see Figure 1). These reusable stainless-steel instruments will be provided in disposable labeled white boxes. In addition, Zip-stitch[™] clips are provided in cartons each containing five individually pouched and labeled clips. Clip pouches are opened by peeling apart at the indicated chevron and removing the clip from the contained stability mounting card. See instructions for use, contained in both device boxes, for additional information.

The test product, Zip-stitch™, is manufactured and provided by the sponsor:

ZSX Medical LLC [name]

The reference product, VICRYL[™] suture, is manufactured by Ethicon Inc:

Ethicon Inc, Somerville, New Jersey

